7.4. Serious Adverse Event Reporting

All SAEs, irrespective of relationship to IP, must be reported within 24 hours of the Investigator knowledge of the event to the Sponsor or CRO. In particular, if the SAE is fatal or life-threatening, notification to the Sponsor must be made immediately, irrespective of the extent of available AE information. This timeframe also applies to follow-up information on previously forwarded SAE reports as well as to the initial and follow-up reporting of exposure during pregnancy and exposure via breast feeding cases.

Relevant medical records should be provided to the Sponsor or CRO as soon as they become available; autopsy reports should be provided for deaths if available. Should an Investigator be made aware of an SAE occurring any time after the reporting period, it must be promptly reported.

All SAEs that have not resolved by the end of the study, or that have not resolved upon discontinuation of the patient's participation in the study, must be followed until any of the following occurs:

- The event resolves.
- The event stabilizes.
- The event returns to baseline, if a baseline value/status is available.
- The event can be attributed to agents other than the IP or to factors unrelated to study conduct.
- It becomes unlikely that any additional information can be obtained (patient or health care practitioner refusal to provide additional information, lost to follow-up after demonstration of due diligence with follow-up efforts).

7.5. Pregnancies

All initial reports of pregnancy must be reported to the Sponsor within 24 hours of the Investigator knowledge of the event using the appropriate pregnancy form.

For IP, an exposure during pregnancy occurs if:

- A female becomes, or is found to be, pregnant either while receiving or having been directly exposed (e.g., environmental exposure) to the IP, or the female becomes, or is found to be, pregnant after discontinuing and/or being directly exposed to the IP (maternal exposure) for 28 days after last dose of or exposure to IP.
- A male partner of a pregnant female has been exposed to the IP, either due to treatment or environmental exposure, within 3 months prior to the time of conception and/or is exposed during his partner's pregnancy (paternal exposure).

If any study patient or study patient's partner becomes or is found to be pregnant during the study patient's treatment with the IP or exposure as defined above, the Investigator must submit this information on a Pregnancy form to the Sponsor (or its designated representative). In addition, the Investigator must submit information regarding environmental exposure to an IP in a pregnant woman (e.g., a patient reports that she is pregnant and has been exposed to a cytotoxic product by inhalation or spillage) using the Pregnancy form. This must be done irrespective of whether an AE has occurred and within 24 hours of awareness of the pregnancy. The information submitted should include the anticipated date of delivery (see following information related to induced termination of pregnancy).

Follow-up is conducted to obtain pregnancy outcome information on all exposure during pregnancy reports with an unknown outcome. The Investigator will follow the pregnancy until completion or until pregnancy termination (e.g., induced abortion) and then notify the Sponsor or its designated representative of the outcome as a follow-up to the initial Pregnancy form. In the case of a live birth, the structural integrity of the neonate can be assessed at the time of birth. In the event of a termination, the reason(s) for termination should be specified and, if clinically possible, the structural integrity of the terminated fetus should be assessed by gross visual inspection (unless pre-procedure test findings are conclusive for a congenital anomaly and the findings are reported).

If the outcome of the pregnancy meets the criteria for immediate classification as an SAE (e.g., ectopic pregnancy, spontaneous abortion, intrauterine fetal demise, neonatal death, or congenital anomaly [including that in a live born, a terminated fetus, an intrauterine fetal demise, or a neonatal death]), the Investigator should follow the procedures for reporting SAEs.

Additional information about pregnancy outcomes that are classified as SAEs follows:

- "Spontaneous abortion" includes miscarriage and abortion.
- All neonatal deaths that occur within 1 month of birth should be reported, without regard to causality, as SAEs. In addition, infant deaths after 1 month should be reported as SAEs when the Investigator assesses the neonatal death as related to exposure to IP.

Additional information regarding the exposure during pregnancy may be requested by the Investigator. Follow-up information regarding the outcome of the pregnancy and any postnatal sequelae in the infant will be required.

8. Statistical Methods and Determination of Sample Size

8.1. Statistical and Analytical Plans

A brief description is given of the planned analysis methodology. Detailed descriptions of the statistical analysis methods and data conventions will be provided as a separate document; i.e., the Statistical Analysis Plan (SAP). The SAP may also include additional exploratory analyses not explicitly mentioned in the following sections. A detailed SAP will be finalized prior to final databased lock. Any significant changes to the analyses described in this protocol will be highlighted in the SAP and the Clinical Study Report.

8.2. Determination of Sample Size

Assumption of sample size calculation:

- Study design: Simon's optimal two stage design^{1,2}
- Type I error (one-sided): 10%
- Power: 80%
- Response probability of null hypothesis (P0): 0.10
- Response probability of SCB01A (P1): 0.25

According to these hypotheses, up to 58 patients need to be recruited into the study (including patients from the run-in phase). At least 6 patients are required to achieve complete response (CR), PR or SD at the end of the 9th week after first treatment with SCB01A for the study to meet its primary objective. The trial will be discontinued if DC is observed in two or fewer patients after the Stage 1 interim analysis review.

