Number of Planned Patients:	
Up to 64 patients will be enrolled, consisting up to 30 patients in the run-in phase; 7 to 10 patients at Stage 1 of Phase II at the 'Optimal Dose' and 21 patients in Stage 2 of Phase II. During the run-in phase, any patients who do not complete the 3 cycles of study treatment, and do not experience a DLT, will be replaced, while no patients will be replaced during Phase II.

Diagnosis and main criteria for enrolment:	
Inclusion Criteria:
 
 1. Aged \geq20 years; 2. Signed informed consent obtained prior to initiation of any study-specific procedures and treatment; 3. Histological or cytological confirmed squamous cell carcinoma of head and neck; 4. Patients with non-resectable, unfeasible radiotherapy, recurrent or metastatic head and neck squamous cell carcinoma, after previous treatment with a platinum agent; 5. At least one measurable tumor lesion toas defined by RECIST version 1.1 as assessed by the investigator (local radiological image assessment); 6. Eastern Cooperative Oncology Group (ECOG) Performance Status (PS) 0-2; 7. Life expectancy of 12 weeks or longer; 8. Patients must have radiological measurable or clinically evaluable disease. Physical examination and radiographic studies have to be performed within 28 days of enrolment; 9. Concurrent local therapy is not allowed, but concurrent palliative radiation therapy to non-measurable sites of disease such as painful bone metastasis is permitted; 10. All eligible patients of childbearing potential have to use

	
effective contraception; that is, double barrier contraceptive methods;
 
11. Documented progressive disease within past 6 months;
 
12. Adequate bone marrow reserve, cardiac, renal and liver function:
 
a. Absolute neutrophil count (ANC) $> 1.5 \times 10^9/L$;b. White blood cell (WBC) $> 3 \times 10^9/L$c. Platelet count $> 75 \times 10^9/L$;d. Hemoglobin $> 9 \text{ g/dL} (> 5.6 \text{ mmol/l})$;e. Prothrombin time (PT)/international normalized ratio (INR) $\leq 1.5 \times$ upper limit of normal (ULN)f. Creatinine clearance (Cockcroft & Gault formula) $> 50 \text{ mL/min}$;g. Alanine aminotransferase (ALT, SGPT) and aspartate aminotransferase (AST, SGOT) and Alkaline Phosphatase (ALP) $< 3 \times$ ULN.h. Serum albumin $\geq 3 \text{ g/dL}$;i. INR $\leq 1.5 \times$ ULNj. Total Bilirubin $\leq 1.5 \times$ ULN
--	---

Exclusion Criteria:

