	
only).
 
Details of any other populations for analysis will be described in the statistical analysis plan (SAP).
 
Statistical Analysis
 
Assumption of sample size calculation:
 
• Study design: Simon's optimal two stage design^{1,2}• Type I error (one-sided): 10%• Power: 80%• Response probability of null hypothesis (P0): 0.10• Response probability of SCB01A (P1): 0.25 
According to these hypotheses, up to 64 patients need to be recruited into the study (including patients from the run-in phase). At least 6 patients are required to achieve CR, PR or SD at the end of the 9th week after first treatment with SCB01A for the study to meet its primary objective. The trial will be discontinued if DC is observed in one or none patients after the Stage 1 Disease Controls Review.
 
Stopping rule: stopped early for futility if less than 2/13 (including 0 or 1 of 13 patients) show DCR in Stage 1 of Phase II with no further investigation of the drug if less than 6/34 achieve DCR by the end of Stage 2 of Phase II.
 
Both according to FAS and PP approaches (all enrolled patients who meet the eligibility criteria and do not present major deviations during the study) will be included in the analyses. The conclusion will be summarized according to analyses of PP population. Inferential analysis results will be expressed as point estimates and their 95% confidence intervals (CIs). To be consistent with the sample size calculation, the 90% CI will also be presented. Analyses will be carried out using SAS® Software, version 9.3 or higher (SAS Institute, Cary, North Carolina, USA).
 
All time-to-event endpoints, including OS time and PFS, will be reported in days (median with 95% CI and range) and calculated using Kaplan-Meier methods. Patients who have not progressed or who have died at the time of the analysis will be censored at the last disease assessment date.
 
PK Evaluations
 
The blood samples will be assayed for SCB01A and PK parameters (area under the plasma concentration-time curve from time zero to time t [AUC_{0-t}], area under the plasma concentration-time curve from time zero to infinite time [$AUC_{0-\infty}$], and maximum plasma concentration [C_{max}], clearance [CL], volume of distribution [V_d], half-life [$t_{1/2}$], elimination

--	--

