2.4. Sample Size

Run-in Phase I (Dose Escalation Phase)

No formal statistical calculation of sample size was conducted for run-in phase I (dose escalation phase). This was a standard 3 + 3 up/down dose escalation design. The sample size was empirical. The small numbers per cohort in this phase were not intended for statistical hypotheses. Only five (5) subjects were recruited in run-in phase I when the trial was terminated.

Phase II

The sample size in phase II was based on Simon's optimal two-stage design to test that the disease control rate in subjects treated with SCB01A was less than or equal to 10% (null hypothesis), or at least 25% (alternative hypothesis), with a significance level of 0.10 (one-sided) and power of 80%. As mentioned above, in stage 1 of phase II, 13 subjects would be needed, and 21 subjects would be needed in stage 2 of phase II, with a total of 34 subjects (13 + 21) needed in phase II. There was no recruitment for phase II.

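### The protocol says its design hypotheses need 58 patients in Section 8.2 and 64 in the synopsis; they need 34 at the Optimal Dose, and the two totals are unreconciled enrolment ceilings.

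*Protocol*

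**What the plan says.** Protocol Section 8.2 lists the design inputs ("Study design: Simon's optimal two stage design", one-sided type I error 10%, power 80%, "Response probability of null hypothesis (P0): 0.10", "Response probability of SCB01A (P1): 0.25"). It then says that on these hypotheses "up to 58 patients need to be recruited into the study (including patients from the run-in phase").

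The synopsis, under Statistical Methods, lists the same inputs and repeats the sentence with another number: "up to 64 patients need to be recruited into the study (including patients from the run-in phase"). Under Number of Planned Patients it says "Up to 64 patients will be enrolled, consisting up to 30 patients in the run-in phase", with 7 to 10 further patients in Stage 1 and 21 in Stage 2. Run-in patients who neither complete three cycles nor have a DLT are replaced; Phase II patients are not.

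Protocol Section 3.1 sets Stage 1 at 13 patients, counting those already treated at the Optimal Dose in the run-in. SAP Section 2.4 gives the Simon sample size, "with a total of 34 subjects (13 + 21) needed in phase II". The number 34 does not appear in protocol Section 8.2.

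**The concern.** Section 8.2 is where a reader looks for the sample size and its derivation. It offers a number that the listed inputs do not produce, and the synopsis offers a different one for the same inputs. Both are current text, so this is not a difference between an amendment log and the protocol.

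Two things are at stake. First, the sample size that supports the stated error rates is missing from the section that should state it. Second, sites and ethics committees have two ceilings, so it is unclear whether a 59th patient is authorised. If the lower one were enforced after run-in replacements had used up places, Phase II could fall short of 34, and the design has little power to spare.

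**Working it through.** **1. What the hypotheses give.** The inputs are those in Section 8.2. The boundaries are those in the synopsis and SAP Section 2.1: stop after Stage 1 with 0 or 1 of 13; succeed with at least 6 of 34. With X1 ~ Bin(13, p) and X2 ~ Bin(21, p),

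P(success | p) = Σ over x = 2 to 13 of P(X1 = x) · P(X2 ≥ 6 − x).

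- At p = 0.10: 0.2448 × 0.1520 + 0.0997 × 0.3516 + 0.0277 × 0.6353 + 0.0055 × 0.8906 + 0.0009 = 0.096 (exact 0.0957).
- At p = 0.25: 0.2059 × 0.8083 + 0.2517 × 0.9255 + 0.2097 × 0.9810 + 0.1258 × 0.9976 + 0.0802 = 0.811.
- Expected size under P0: P(X1 ≤ 1) = 0.6213, so 13 + 0.3787 × 21 = 20.95.

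An exact search over two-stage designs with alpha at most 0.10 and power at least 0.80 returns this design as the one with the smallest expected size. The minimax design has 31 patients. The SAP's 34 is reproduced; 58 and 64 are not.

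Section 8.2 itself has a different Stage 1 stop, at two or fewer. That conflict is a separate point. With that stop the power is 0.644 even with all 34 enrolled.

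**2. Where 58 comes from.** Stage 1 tops the Optimal Dose cohort up to 13, so before replacements

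total = (run-in patients at other doses) + 13 + 21.

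The longest run-in path has five cohorts (Doses 1, 2, 3, 4, 3a). Four of them lie outside the Optimal Dose, with at most 6 patients each: 24 + 34 = 58. Written as the synopsis does:

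- 6 at the Optimal Dose: 30 + 7 + 21 = 58.
- 3 at the Optimal Dose: 27 + 10 + 21 = 58.

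Adding the listed maxima, 30 + 10 + 21 = 61, describes a case that cannot occur: 10 in Stage 1 requires a three-patient Optimal Dose cohort, and the run-in is then at most 27.

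**3. Where 64 comes from.** 20% of 30 is 6, and 58 + 6 = 64. The 20% allowance stands only in the amendment log. It is used here to explain the number; its absence from the current text is not counted as an error by comparison with the log. The consequence is internal to the current synopsis: its listed parts do not sum to its total.

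**4. Room for replacements under a ceiling of 58.**

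| Run-in path, cohorts full | Total before replacements | Places left under 58 |
|---|---|---|
| Five cohorts, Dose 1 with 6 | 24 + 34 = 58 | 0 |
| Five cohorts, Dose 1 with 3 | 21 + 34 = 55 | 3 |
| All shorter paths | 43 to 52 | 6 to 15 |

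Cohorts that stop at 3 leave more room.

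**5. If the ceiling did bind.** Suppose Stage 2 were cut by k patients with both boundaries kept. The documents do not say this would happen. Using the formula in step 1 with 21 − k in Stage 2:

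| Patients lost (k) | At the Optimal Dose | Power |
|---|---|---|
| 0 | 34 | 81.1% |
| 1 | 33 | 79.8% |
| 2 | 32 | 78.4% |
| 3 | 31 | 76.7% |
| 4 | 30 | 74.8% |
| 5 | 29 | 72.6% |
| 6 | 28 | 70.0% |

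**The case against.** Both totals are worded as upper limits that include the run-in, so they count something different from the Simon sample size, and 34 is available in the SAP. That is right. The design parameters, the stage sizes and the final boundary of 6 of 34 are untouched. What remains is that Section 8.2 and the synopsis attribute the ceilings to the hypotheses, and that they disagree.

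A reader might infer that a ceiling of 58 cannot absorb run-in replacements without losing power. The documents do not support that in general. Only the longest path with full cohorts leaves no room. SAP Section 1 reports five patients enrolled in all, and SAP Section 2.1 places them at Doses 1 and 2, so a six-patient Dose 1 cohort did not occur and three places would have been free even on the longest path. Nothing says that Stage 2 would be shortened: it is fixed at 21 further patients, and protocol Section 9.10.1 provides for amendments.

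A reader might also take the six successes required in Section 8.2, which come straight after 58 with no denominator, as six out of 58 or 64, and conclude that the 10% type I error is lost. That does not hold either. The synopsis, Section 8.8 and SAP Section 2.1 all set the final rule at 6 of 34, and no place sets it against a larger number.

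**Conclusion.** The inconsistency is certain from the text: 58 against 64 in the same sentence, neither derivable from the stated inputs, which give 34 (13 + 21) with exact alpha 0.096 and power 0.811. A stated sample size is therefore wrong, and the synopsis total does not equal the sum of its parts.

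The effect on power is conditional. It needs the longest run-in path with full cohorts, or more replacements than a shorter path leaves room for; the lower ceiling being followed; and Stage 2 being cut rather than the ceiling amended. The loss would then run from 81.1% to 79.8% for one patient and to 70.0% for six, the last resting on the 20% replacement assumption. No loss of type I error control follows. The trial ended in the run-in with no Phase II recruitment, so the point concerns the plan and how it is reported, not any result.

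**What to change.** In Section 8.2 and in the synopsis, state that the Simon design requires 34 patients at the Optimal Dose (13 in Stage 1, including run-in patients treated at that dose, plus 21 in Stage 2), and that success means disease control in at least 6 of those 34.

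Separately, give one total enrolment ceiling in every place and do not attribute it to the hypotheses. List its parts (run-in, run-in replacements, Stage 1, Stage 2) so that they sum to it, and state the replacement assumption. For example, if the 20% allowance is kept, 30 + 6 + 7 + 21 = 64.

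The cost is protocol wording, with no patients beyond the 64 already in the synopsis. As the trial has ended, the same statement can go in the sample-size section of the clinical study report.

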Phase II (The continuation phase)

After the Optimal Dose was determined in the run-in phase, a total number of 13 patients (including patients received Optimal Dose in the run-in phase) will be enrolled for stage 1 to receive 3 cycles of i.v. administration of SCB01A at Optimal Dose.

A safety committee review will be performed after stage 1 with the patients who completed 3 cycles of SCB01A treatment at the Optimal Dose. If more than two disease controls (DCs) are observed, another 21 patients will be enrolled into Stage 2 at the same dose level.

No patients will be replaced in the continuation phase (Phase II).

[figure not shown]

Figure 2: Schematic Study Design

All patients will be treated until occurrence of progressive disease, intolerable adverse events (AEs)/toxicity, consent withdrawal or death. After discontinuation of study treatment, all patients will be followed for survival and disease-specific therapies of the clinician's choice. Follow-up visits will be scheduled every 3 weeks for 9 weeks, thereafter every 9 weeks until the end of the study.

The study will be terminated 36 weeks after the last patient has received their 1st treatment with SCB01A.

Safety monitoring committee:

A safety monitoring committee will be established to:

- Evaluate all AEs, and safety laboratory data for the run-in phase;

- Decide on the recommended dose regimen of SCB01A for Phase II.

The schedule of assessments for the run-in phase and Phase II, stages 1 and 2 is shown in detail in Table 1 and Table 2, respectively. The results of protocol specific assessments and procedures will be recorded in the source documents for the patients and on the appropriate page of the electronic case report form (eCRF). The different study days are described below.

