8.5. Efficacy Analysis

The primary efficacy analysis will be performed to assess the DCR and secondary efficacy analysis will be performed to assess the PFS and overall survival rate.

Patients will be considered evaluable for DCR in this study if they fulfill the criteria for evaluation according to RECIST v1.1, i.e., those patients who undergo a baseline disease assessment within 4 weeks of treatment initiation, and who undergo at least 1 disease assessment on-study:

- DCR is defined as the percentage of patients who have achieved CR, PR and SD at a particular time point after first treatment, according to RECIST v1.1.
- PFS is defined as the time from the start of treatment up to the date of first progression based on RECIST v1.1, second primary malignancy or death from any cause, whichever occurs first.
- Overall survival rate is defined as the percentage of patients who are still alive at 36 weeks after first treatment with SCB01A.

Inferential analysis results will be expressed as point estimates and their 95% CIs. To be consistent with the sample size calculation, the 90% CI will also be presented for the primary endpoint. Analyses will be carried out using SAS® Software, version 9.3 or higher (SAS Institute, Cary, North Carolina, USA).

All time-to-event endpoints, including overall survival time and PFS, will be reported in days (median with 95% CI and range) and calculated using Kaplan-Meier methods. Patients who have not progressed or who have died at the time of the analysis will be censored at the last disease assessment date.

The study will be stopped early for futility if less than three DCRs are observed following the completion of the first stage of Phase II. In addition, no further investigation of the drug will be pursued if less than 6 patients achieve DCR by the end of Stage 2 of Phase II.

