8.8. Interim Analysis

An interim statistical analysis will be performed following the completion of stage 1, Phase II. If more than two DCs are observed, an additional 21 patients will be enrolled into Stage 2 at the same dose level. The study will be stopped early for futility if less than 3 DCRs are observed following the completion of the first stage of Phase II with no further investigation of the drug if less than 6/34 achieve DCR by the end of Stage 2 of Phase II.

9. Study Management

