16. Interim and Final Analysis	31
16.1. Interim Analyses	31
16.2. Final Analysis (End of Study).....	31
17. Software	32
18. Tables	33
19. Listings	35
20. Figures	37
21. References	39

1. Introduction

The following Statistical Analysis Plan (SAP) provides the outline for the statistical analysis of the data from SCB01A-21 study. This SAP is based on the study protocol version 3.0 (dated on 25Jul2016).

The planned analyses identified in this SAP may be included in clinical study reports (CSRs), regulatory submissions, or future manuscripts. Also, post hoc analyses not necessarily identified in this SAP may be performed to further examine study data. Any post hoc, or unplanned, exploratory analyses performed will be clearly identified as such in the final CSR.

Note: This study was designed to have two phases, namely run-in phase I (dose escalation phase) and phase II. This study was terminated early in run-in phase I, with eight (8) subjects screened and five (5) subjects enrolled. There was no recruitment for phase II. In light of the small number of subjects enrolled in this study, the SAP will focus on safety data analysis. Efficacy data will be conducted only if there are enough subjects/events, as appropriate, for the analysis methods.

2. Project Overview

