The phase II followed a Simon's optimal two-stage design to test the disease control rate (including complete response, partial response and stable disease) in subjects treated with SCB01A was at least 25% (alternative hypothesis). In the first stage of phase II, a total of 13 subjects would be enrolled at the optimal dose level, including those already enrolled at the optimal dose level from Run-in Phase I. If 1 or fewer patient was observed with disease control response in the stage 1 of phase II, then the study would be stopped for futility, with disease control rate concluded to be less than or equal to 10% (null hypothesis). Otherwise, the phase II would enter into its stage 2, in which an additional 21 subjects would be enrolled at the optimal dose level. If 6 or more subjects were observed with disease control response out of the 34 subjects enrolled (13 + 21) in the stage 2, the disease control rate in subjects treated with SCB01A would be concluded to be at least 25%. Otherwise, the disease control rate in subjects treated with SCB01A would be concluded to be less than or equal to 10%, and further investigation of the investigational treatment was not warranted.

The study was terminated without any recruitment for phase II.

Subjects would receive the recommended dose of mono-therapy of SCB01A for 9 weeks (3 weeks*3 cycles) or until disease progression, intolerable toxicity, consent withdrawal or death, whichever occurs first. DLT and safety would be followed in each phase of study. Pharmacokinetic (PK) would be performed on subjects enrolled in the run-in phase, with PK blood samples taken immediately pre-infusion then at 2, 3, 4, 6, 10, 21 and 24 hours after the start of infusion on Days 1 and 8 of Cycles 1, 2 and 3. Bioanalytical measurements and health outcome data (EORTC QLQ-C30 and EORTC QLQ-H&N35) were to be collected. Tumor response would be assessed by using computerized tomography (CT) or MRI scans according to RECIST v1.1 at baseline, and every 3 cycles prior to the next cycle until progression of the disease.

2.2.Objectives

Run-in Phase I (Dose Escalation Phase)

Primary objective:

- To determine the optimal dose for 3 cycles of i.v. administration of SCB01A on Days 1 and 8 of each cycle in a 3-week cycle

Secondary Objective:

- To evaluate the safety and toxicity for 3 cycles of i.v. administration of SCB01A on Days 1 and 8 of each cycle in a 3-week cycle
- To assess the PK profile of SCB01A of subjects in the run-in phase.

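### Four protocol sections stop after Stage 1 at two or fewer disease controls, but the synopsis and SAP stop at none or one; the stricter rule has 64.4% power, not 80%

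*Protocol*

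**What the plan says.** **Stop at two or fewer.** Four sections of the protocol body require at least three disease controls before Stage 2 opens:

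- Section 8.2: "The trial will be discontinued if DC is observed in two or fewer patients after the Stage 1 interim analysis review".
- Section 3.1: "If more than two disease controls (DCs) are observed, another 21 patients will be enrolled into Stage 2 at the same dose level".
- Section 8.5: "The study will be stopped early for futility if less than three DCRs are observed".
- Section 8.8: "If more than two DCs are observed, an additional 21 patients will be enrolled into Stage 2 at the same dose level". It then repeats the rule as a stop below three.

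**Stop at none or one.** The synopsis, under Statistical Methods, has a sentence almost identical to the one in 8.2 but with a different number: "The trial will be discontinued if DC is observed in one or none patients after the Stage 1 Disease Controls Review". Its stopping rule says the same with a denominator: "stopped early for futility if less than 2/13 (including 0 or 1 of 13 patients) show DCR in Stage 1 of Phase II". SAP Section 2.1 agrees: "If 1 or fewer patient was observed with disease control response in the stage 1 of phase II", the study stops for futility; otherwise it goes on to Stage 2.

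Everything else in the design is common to both versions: 13 patients in Stage 1, 21 more in Stage 2, and success at 6 or more of 34. Section 8.2 and the synopsis list the same assumptions: Simon's optimal two-stage design, one-sided type I error 10%, power 80%, P0 = 0.10 and P1 = 0.25.

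**Total size.** From these same hypotheses, Section 8.2 derives a maximum of 58 patients and the synopsis a maximum of 64. SAP Section 2.4 gives 34 for Phase II.

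**The concern.** Exactly 2 disease controls among 13 is a stop under one set of passages and a continue under the other. This is not a difference between current text and an amendment log; all the passages are operative. The sections titled Determination of Sample Size and Interim Analysis, where one would look for the rule, carry the stricter version.

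The two boundaries cannot both come from the assumptions in 8.2. If the stricter one does not, the section that states 80% power prints a rule that fails to deliver it, and an active drug is more likely to be abandoned after Stage 1. The SAP presents the 0-or-1 rule as the planned design and does not mention that four protocol sections state another.

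**Working it through.** **Inputs.** P0 = 0.10, P1 = 0.25, one-sided alpha 10% and power 80% (Protocol 8.2); n1 = 13 (Protocol 3.1, synopsis, SAP 2.1); n2 = 21, so n = 34 (SAP 2.4); success at 6 or more of 34 (synopsis, Protocol 8.8). Sections 8.2, 8.5 and 8.8 do not print the Stage 1 denominator, so 13 is taken from the other passages. All 13 and all 34 patients are assumed to count.

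**Formula.** If the trial stops at r1 or fewer in Stage 1,

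P(success | p) = Σ over x > r1 of P(Bin(13, p) = x) × P(Bin(21, p) ≥ 6 − x).

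**Contribution of each Stage 1 result.**

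| x of 13 | P(x), p = 0.25 | P(reach 6), p = 0.25 | Product | P(x), p = 0.10 | P(reach 6), p = 0.10 | Product |
|---|---|---|---|---|---|---|
| 2 | 0.2059 | 0.8083 | 0.1664 | 0.2448 | 0.1520 | 0.0372 |
| 3 | 0.2517 | 0.9255 | 0.2329 | 0.0997 | 0.3516 | 0.0351 |
| 4 | 0.2097 | 0.9810 | 0.2057 | 0.0277 | 0.6353 | 0.0176 |
| 5 | 0.1258 | 0.9976 | 0.1255 | 0.0055 | 0.8906 | 0.0049 |
| 6 or more | 0.0802 | 1 | 0.0802 | 0.0009 | 1 | 0.0009 |

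**Reproducing the stated 80%.** With the synopsis and SAP rule, all five rows count: power 0.8108 and alpha 0.0957. Both meet the stated 80% and 10%. An exhaustive search of two-stage designs with total size 15 to 45, exact alpha at most 0.10 and power at least 0.80, gives this same design as the one with the smallest expected size under P0: stop at 1 or fewer of 13, fail at 5 or fewer of 34, expected size 13 + 21 × (1 − 0.6213) = 20.95.

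**The rule in 3.1, 8.2, 8.5 and 8.8.** The first row drops out: power 0.8108 − 0.1664 = 0.6444, and alpha 0.0957 − 0.0372 = 0.0585.

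| | Stop at 0 or 1 of 13 | Stop at 0 to 2 of 13 |
|---|---|---|
| Alpha | 9.6% | 5.9% |
| Power | 81.1% | 64.4% |
| P(early stop), true rate 25% | 12.7% | 33.3% |
| P(early stop), true rate 10% | 62.1% | 86.6% |

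**Can another final cut-off rescue the stricter rule?** No. At a 25% rate the chance of passing Stage 1 is 1 − 0.3326 = 0.6674, which caps power whatever happens later. The best final cut-off that keeps alpha at or below 10% is 5 or more of 34: alpha 0.0945, power 0.6621.

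**How often the conflict would bite.** Exactly 2 of 13 has probability 20.6% at a 25% rate and 24.5% at a 10% rate.

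**Total size.** The synopsis allows up to 30 run-in patients, then 7 in Stage 1 if the optimal-dose cohort had 6, or 10 if it had 3, then 21. The largest path is 30 + 7 + 21 = 58, or equally 27 + 10 + 21 = 58. The synopsis figure of 64 is 6 higher. The amendment summary mentions a 20% replacement allowance in the run-in; 20% of 30 is 6, and 58 + 6 = 64. That clause is absent from the synopsis and from 8.2. Neither 58 nor 64 follows from the Simon hypotheses, which give 34.

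**The case against.** The strongest point is practical. The SAP introduction reports: "This study was terminated early in run-in phase I, with eight (8) subjects screened and five (5) subjects enrolled". Phase II recruited nobody, no Stage 1 look took place, and rewording a closed protocol changes nothing in the conduct of the trial. This stands, and it limits the consequence to how the planned design is reported.

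Second, Section 8.1 defers detailed methods to the SAP, which states one coherent rule matching the synopsis, so the planned design can be identified. That is partly right. But 8.1 also promises that significant changes from the protocol will be highlighted in the SAP and the study report, and the SAP is silent on the four conflicting sections.

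Third, the stricter rule errs on the safe side for false positives, since alpha falls to 5.9%. True; the harm is lost power only.

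Fourth, the exact figures assume full denominators. Section 3.1 bases the review on patients who completed three cycles, Section 8.5 limits disease control to evaluable patients, and nobody is replaced in Phase II. Fewer counted patients would change the percentages, but the opposite instructions at two disease controls would remain.

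Fifth, the total of 64 has a plausible origin in the replacement allowance. That explains the number, but the operative text still gives two totals and omits the allowance.

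**Conclusion.** The concern holds. The operative text contains two Stage 1 boundaries, and only the one in the synopsis and SAP 2.1 agrees with the stated assumptions. The boundary in Protocol 3.1, 8.2, 8.5 and 8.8 costs 16.6 points of power (81.1% to 64.4%, from unrounded values) and cannot reach 80% with any final cut-off. With a true disease control rate of 25%, it stops about one trial in three instead of one in eight.

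These are exact binomial figures and assume that 13 and 34 patients are all counted. No decision in this trial was affected. What is left is a defect in the planned primary decision rule that a reader of the results could not resolve without recalculating. The totals of 58 and 64 are a secondary inconsistency.

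**What to change.** - In Protocol 3.1, 8.2, 8.5 and 8.8, state that the study stops if 0 or 1 of 13 patients have disease control and continues if 2 or more do, as in the synopsis and SAP 2.1. Give the Stage 1 denominator each time, and quote the exact alpha (9.6%) and power (81.1%).
- In 8.2 and the synopsis, give 34 as the Simon sample size at the Optimal Dose. State separately one overall maximum whose parts add up: 58 before run-in replacements, or 64 if the replacement allowance is included and spelled out.
- Because the study has ended, the clinical study report can do this in one paragraph: say which boundary was planned, and that the protocol text was inconsistent.

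The cost is wording in four sections plus the total-size sentences, or that one paragraph. It needs no extra patients and no re-analysis.
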